7.3. Exploratory Endpoints

7.3.1. Other Safety Parameters

Additional safety parameters include clinical laboratory parameters (hematology, serum chemistry, LFTs, urinalysis, and coagulations), vital signs, 12-lead ECGs, renal ultrasounds and physical examinations. All additional safety parameters will be analyzed using the Safety Analysis Set.

Clinical Laboratory Parameters: Clinical laboratory parameters will be expressed in SI units. Laboratory data collected and recorded below the LLOQ will be set to the lower limit of quantification for the calculation of summary statistics. Summaries will only include data from the central laboratory (except eGFR as this is summarized in efficacy). Key laboratory parameters will be graded according to NCI CTCAE v5.0.

Laboratory parameters (hematology, chemistry, liver function tests, coagulation and urinalysis), which are continuous variables, will each have a tabular summary of descriptive statistics at each scheduled visit. Descriptive statistics include actual value, change from baseline and percent change from baseline at each scheduled visit.

Shift tables will be generated to summarize shifts from baseline categories to the worst post-baseline categories with directionality specified for any labs which could be reported in either direction (e.g. above threshold or below threshold).

Clinical laboratory tests with normal ranges will be classified as Low, Normal, and High. For these tests, abnormal values will be flagged in the listings with grade appended (e.g. H1 will represent that the lab reported met the threshold of high range with grade 1).

For hematology and chemistry laboratory assessments, summary tables of potentially clinically significant abnormalities will also be provided.

All laboratory data will be presented in data listings. Out of range laboratory results will be identified in listings.

Liver Function Tests (LFTs): A listing will be generated for all patients with abnormal liver function tests as defined by ALT $>3 \times$ ULN, AST $>3 \times$ ULN or total bilirubin $>2 \times$ ULN at any visit.

A tabular summary for LFTs will be generated to summarize the number and associated percentage of patients in each of the categories at any post-baseline visit:

- ALT >1 and ≤ 3 , ALT >3 and ≤ 5 , ALT >5 and ≤ 10 , ALT >10 and ≤ 20 , ALT $>20 \times$ ULN
- AST >1 and ≤ 3 , AST >3 and ≤ 5 , AST >5 and ≤ 10 , AST >10 and ≤ 20 , AST $>20 \times$ ULN
- ALT or AST >1 and ≤ 3 , ALT or AST >3 and ≤ 5 , ALT or AST >5 and ≤ 10 , ALT or AST >10 and ≤ 20 , AST or ALT $>20 \times$ ULN
- WNL, ALP $>1.5 \times$ ULN
- Total bilirubin >1.5 and ≤ 2 , total bilirubin >2 and ≤ 3 , total bilirubin >3 and ≤ 5 and total bilirubin >5

eDISH plots of peak total bilirubin at any time versus peak ALT or AST at any time will also be presented.

Vital Signs: Descriptive statistics for each vital sign (e.g. systolic blood pressure, diastolic blood pressure, pulse rate, body temperature, respiratory rate, height, weight, body mass index) will be summarized at scheduled visits. Summaries will include actual values and changes from baseline. A summary table of potentially clinically significant shifts in vital signs will also be generated separately for pediatric patients (<18 years old) and adult patients.

For any patient <18 years of age at screening, the modified z-score will be calculated for height, weight and body mass index (BMI) according to the CDC growth chart f. Descriptive statistics of z-scores by visit and treatment arm will be summarized. A tabular summary of the proportion of patients with z-scores at various cut-points (e.g., above and below 2 SD) will also be summarized.

A separate listing of vital sign data will be generated. Per patient plots of z-scores over time for those patients <18 years of age at screening in Study 001 will also be generated.

12-lead ECGs: Electrocardiogram (ECG) parameters include rhythm, ventricular rate, PR interval, QRS duration, QT interval, and QTc interval. Corrected QT interval (QTc), if not collected, will be calculated using the Fridericia's correction formula.

$$\text{Fridericia's cube-root corrected QT: } \text{QTcF (ms)} = \text{QT (ms)} \times \sqrt[3]{\frac{\text{HR(bpm)}}{60}}.$$

The number and percentage of patients with normal, abnormal, and clinically significant abnormal results at baseline and each time point will be summarized.

For electrocardiogram parameters, these will be summarized using descriptive statistics for actual values and for changes from baseline by scheduled time of evaluation.

Baseline, post baseline maximum QTcF and post baseline maximum change from baseline in QTcF during the study will be summarized with descriptive statistics. The incidence of notable ECG changes from baseline in maximum absolute QTcF, intervals (≤ 450 , > 450 , > 480 , and > 500 ms) over all post-treatment evaluations, as well as in QTcF, maximum changes from baseline (≤ 30 ms, > 30 to 60 ms and > 60 ms) over all post-treatment evaluations will be summarized.

A listing of all ECG data will be provided.

Physical Examinations: During the study, full physical examinations and symptom directed physical examinations will be conducted. If any abnormalities are observed during these physical examinations or worsened from baseline, then this will be recorded on the AE form.

A separate listing per patient will be generated to display the dates and times of the physical examination.

Renal Ultrasounds: During the study, renal ultrasounds will be collected at baseline, Month 12 and Month 24. The number and percentage of patients at baseline with findings of normal, abnormal, not clinically significant, clinically significant will be summarized. In addition, the number and percentage of patients in categories to indicate if a significant change from baseline has been documented will also be summarized at each post-baseline visit. Listings will also be generated.

7.3.2. Characterize the Pharmacokinetics of lumasiran

PK analyses will be conducted using noncompartmental methods using data with intensive plasma and urine PK samples. PK parameters will be calculated using a validated version of Phoenix® WinNonlin.

Population PK analysis of plasma data is planned for all patients in the study and will be described in a separate population PK analysis plan.

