^g Baseline visit 12-lead ECGs are triplicate and will be measured approximately 5 minutes apart. Recordings will be obtained after the patient has rested comfortably in the supine position for approximately 10 minutes. Patients should remain supine between ECGs. ECGs should be obtained at visits to the clinical study center where indicated in the Schedule of Assessments prior to study drug administration (see Section 7.4.4). ECGs do not need to be conducted for interim doses. After Month 12, ECGs will be performed at Months 24, 36, 48, and 54; all postbaseline ECGs will be measured in singlicate.

^h Echo should be performed at Baseline only if the most recent echo was performed \geq 30 days before Day 1. Echo will be performed during the first 12 months only.

ⁱ Pregnancy tests will be performed for women of childbearing potential only. Pregnancy testing should be performed prior to each dose; results of the pregnancy test must be known before ALN-GO1 administration. A serum pregnancy test will be performed at Baseline or after the onset of menarche if the patient was not of childbearing potential at Baseline, and urine pregnancy tests will be performed thereafter, and any time pregnancy is suspected. Patients who become pregnant should inform the clinical study center as soon as a pregnancy is confirmed.

^j Clinical laboratory tests will be evaluated by a central laboratory.

^k Study drug will be administered via SC injection. In patients whose disease progression requires a dialysis regimen, patients will continue on their current dosing regimen (see Section 6.2.2).

^l Blood and urine samples for PK analysis will be obtained at the time points listed in Table 5.

^m During the Baseline visit, the blood sample for PD analysis must be collected within 1 hour predose. In patients who progress to requiring dialysis, when a dialysis session is on same day as scheduled visit, the blood sample for PD analysis must be collected predialysis.

ⁿ Single, 24-hour urine sample collections will be performed before dosing, as indicated. For study visits through the Month 12 visit, urine collections should be completed within 7 days before each study visit. For study visits after the Month 12 visit (ie, Month 18 through the EOS) urine collections should be completed within 14 days before each study visit.

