4. INVESTIGATIONAL PLAN

4.1. Summary of Study Design

This is a multicenter, open-label extension study to evaluate the long-term safety, PK, and PD of subcutaneously administered ALN-GO1 in patients with PH1 who completed Study ALN-GO1-001.

Consented eligible patients will enroll in this study and initially receive subcutaneous (SC) injections of ALN-GO1 at the same dose and regimen as they received in Study ALN-GO1-001. Based on emerging data, the SRC may authorize an alteration of dose and/or dose regimen to one that is no higher than the highest dose evaluated in either Part A or Part B of Study ALN-GO1-001. If such an authorization occurs, dose and/or dose regimen alteration may occur for an individual patient or entire cohort. This alteration may apply to subsequent doses for patients already enrolled and previously dosed in the study and/or to the initial dose and regimen for patients who have not yet been dosed in this study. Patients will be assessed for safety at each study visit.

PD assessments will be completed quarterly over the first 12 months on study, and approximately every 6 months thereafter for the study duration. PK assessments will be conducted during the first 12 months on study ([Table 1](#)).

Patients may receive ALN-GO1 as long as they do not fulfill any of the study discontinuation criteria (see [Section 5.3.1](#)) or until ALN-GO1 is commercially available in the patient's territory or the ALN-GO1 development program is discontinued (whichever comes first).

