8.2.6. Pharmacokinetic Analysis

Pharmacokinetic analyses will be conducted using noncompartmental methods.

Pharmacokinetic parameters include, but will not be limited to: C_{max} , t_{max} , $t_{1/2\beta}$, AUC, Fe, CL/F, and V/F. Other parameters may be calculated, if deemed necessary.

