11. APPENDICES

11.1. Pharmacokinetic Assessment Time Points

Table 5 contains a detailed schedule for the collection of blood and pooled urine samples for PK analysis.

Table 5 Pharmacokinetic Time Points

Study Visit	Time Point (hh:mm)	PK Blood	Pooled Urine Collection
Baseline (Day 1)	Predose (within 60 minutes before dosing)	X	
	00:00 (dose)		
	02:00 (± 10 min)	X	
	04:00 (± 10 min)		X (00:00-04:00)
	04:01 (± 10 min)		
	08:00 (± 15 min)	X	X (04:01-08:00)
	08:01 (± 15 min)		
	24:00 (± 30 min)	X	X (08:01-24:00)
Month 6 (Day 169)	Predose (within 60 minutes before dosing)	X	
	00:00 (dose)		
	02:00 (± 10 min)	X	X (00:00-04:00)
	04:00 (± 10 min)		
	04:01 (± 10 min)		X (04:01-08:00)
	08:00 (± 15 min)	X	
Month 12 (Day 337)	Predose (within 60 minutes before dosing)	X	
	00:00 (dose)		
	02:00 (± 10 min)	X	X (00:00-04:00)
	04:00 (± 10 min)		
	04:01 (± 10 min)		X (04:01-08:00)
	08:00 (± 15 min)	X	

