3.2.3. Exploratory Endpoints

- Describe the effect of lumasiran on other safety parameters, including assessments of vital signs, electrocardiograms (ECG), renal ultrasounds, clinical laboratory parameters, and physical examinations
- Assess lumasiran plasma PK parameters including maximum plasma concentration (C_{max}), time to maximum plasma concentration (t_{max}), elimination half-life, area under the curve, fraction of dose excreted in urine, apparent clearance and apparent volume of distribution.
- Change from baseline over the course of the study in the following PD parameters: urinary glycolate excretion, plasma oxalate concentration, plasma glycolate concentration and urine oxalate:creatinine ratio
- Quality of life as assessed by Kidney Disease Quality of Life Questionnaire (KDQOL) for adults (≥ 18 years of age) and the PedsQOL (the generic and ESRD modules) for children (< 18 years of age)
- Incidence of ADA

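### Does the SAP need to fix visits and time windows for the noncompartmental PK parameters, given sampling to 24 h at Baseline but only 8 h at Months 6 and 12?

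*SAP*

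**What the plan says.** The method is in SAP 7.3.2: "PK analyses will be conducted using noncompartmental methods using data with intensive plasma and urine PK samples". That section lists no parameters. SAP 3.2.3 names them, after Cmax and tmax, as "elimination half-life, area under the curve, fraction of dose excreted in urine, apparent clearance and apparent volume of distribution". Protocol 8.2.6 gives method and list together, ending with "AUC, Fe, CL/F, and V/F. Other parameters may be calculated, if deemed necessary". None of the three places gives a visit, an AUC or urine interval, or a rule for accepting a terminal slope, and the word intensive is not defined.

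The sampling is set by protocol Table 5 (section 11.1). Protocol Table 1 labels the row as 24-h urine, but its footnote l says "Blood and urine samples for PK analysis will be obtained at the time points listed in Table 5", so Table 5 governs and the label is a clerical slip. Protocol 4.1 adds that "PK assessments will be conducted during the first 12 months on study", so Baseline, Month 6 and Month 12 are all the PK data there are.

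SAP 7.3.2 also says "Population PK analysis of plasma data is planned for all patients in the study", under a separate analysis plan.

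**The concern.** If the noncompartmental analysis is run at all three visits, and AUC is taken to the last sample, the Baseline value can extend to 24 h while the later values stop at 8 h. Urinary recovery has the same mismatch. Three PK visits in a repeat-dosing study invite the question whether exposure is stable. A table of AUC or fraction excreted by visit could then show a drop after Baseline produced by the sampling schedule alone.

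If intensive means the 24 h Baseline profile only, that problem disappears. But the Month 6 and 12 urine then has no named analysis, because the population PK covers plasma. On either reading the few post-dose plasma samples give weak support for half-life, and hence for AUC to infinity, clearance and volume. At stake would be a misleading description of exposure over time.

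**Working it through.** The documents state no PK figure to reproduce, so the check is a count of samples followed by an illustration.

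**1. Sampling windows (protocol Table 5, as printed)**

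| | Baseline | Months 6 and 12 |
|---|---|---|
| Post-dose plasma | 2, 8, 24 h | 2, 8 h |
| Urine pools end at | 24 h | 8 h |

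The urine windows differ by 24/8 = 3-fold without any model. The plasma windows differ only when the 24 h Baseline sample is quantifiable. Otherwise AUC to the last quantifiable sample ends at 8 h at Baseline as well.

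The table's alignment is uncertain. The 0-4 h urine pool is printed on the 04:00 row at Baseline and on the 02:00 row at the later visits. A 4 h plasma mark could have been lost, but the different end times do not depend on it.

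**2. Size of the mismatch (assumed values throughout)**

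Model: one compartment, first-order absorption at rate ka, ke = ln 2 / half-life, predose concentration zero.

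AUC(0-t) = [ka/(ka - ke)] x [(1 - exp(-ke t))/ke - (1 - exp(-ka t))/ka], in units where AUC to infinity = 1/ke.

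Worked case: absorption half-life 1 h and terminal half-life 4 h, so ka = 0.6931/h and ke = 0.1733/h.

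- AUC(0-8) = 1.333 x (4.328 - 1.437) = 3.855.
- AUC(0-24) = 1.333 x (5.681 - 1.443) = 5.651.
- Ratio = 3.855/5.651 = 0.68.

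Keeping the absorption half-life at 1 h and varying the terminal half-life:

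| Terminal half-life (h) | 2 | 4 | 6 | 8 | 12 | 24 |
|---|---|---|---|---|---|---|
| AUC(0-8)/AUC(0-24) | 0.88 | 0.68 | 0.57 | 0.50 | 0.43 | 0.36 |

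A wider grid crosses ka of 0.15, 0.3, 0.5, 1.0 and 2.0/h with half-lives of 2, 3, 5 and 8 h and drops the 3 cases with ka at or below ke. That leaves 5 x 4 - 3 = 17 cases. The ratio runs from 0.31 to 0.92 and is below 0.80 in 13 of them, one of these at 0.799. In 5 of the 17 the 24 h concentration is under 1% of the observed peak. If it is not quantifiable there, the plasma mismatch vanishes; in the other 12 cases the ratio is 0.31 to 0.73. With constant renal clearance the same ratios apply to urinary recovery over 8 h against 24 h.

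**3. Does a planned analysis use the unequal windows?**

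- SAP 7.3.3 specifies summaries at each scheduled visit, with change and percent change from baseline, for PD parameters.
- SAP 7.3.2 specifies no by-visit PK summary and no change from baseline.
- Protocol 8.2.6 specifies neither, and allows further parameters where needed, so a 0-8 h AUC is already within the plan.
- Plasma kinetics across visits can be addressed by the planned population PK analysis, which does not need equal sampling windows.

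The ratios in step 2 therefore describe a comparison that the plan does not make.

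**The case for a change.** The strongest case for a change is that each reading of intensive leaves something unsaid, the PK Analysis Set in SAP 4.1 requires only one post-dose concentration and so screens out no sparse profile, and a sentence or two would settle the matter at no cost in samples. The 3-fold urine difference needs no assumption. All of that stands as a description of what the SAP leaves out.

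It does not show that a stated rule gives a wrong result. The harm requires someone to tabulate AUC-to-last or recovery by visit without labelling the interval and then read the difference as a change in kinetics. Leaving later urine without a named noncompartmental use is not an error either: protocol 7.3 also collects the samples for possible metabolite analysis.

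The terminal-slope argument is weaker than it looks. Saying that no residual degree of freedom remains at Months 6 and 12 even with a 4 h sample counts only points after the peak, a rule the documents do not contain. If the peak is allowed, samples at 2, 4 and 8 h leave 3 - 2 = 1. In the grid above, a slope through 2 and 8 h gives a half-life in 12 of 17 cases, between 1.02 and 7.1 times the true value. In all 12 the 2 h sample is the higher one, so the slope uses the very point that the counting rule leaves out. The 7.1 comes from one cell (ka 0.3/h, half-life 3 h); the next highest is 3.7. What survives is that half-life, clearance and volume may not be estimable from some profiles. A PK analyst reports that profile by profile.

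**Conclusion.** No change to the plan is needed. The sampling windows do differ, and the SAP does not say which visits are intensive or which interval AUC and fraction excreted cover. But no planned analysis compares these quantities across visits, and the planned population PK covers plasma. Stating the interval beside each AUC and recovery, and marking unsupported half-lives as not estimable, is ordinary practice that analysts follow without an SAP instruction.

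If an unlabelled visit comparison were made, the apparent fall could be large: a ratio of 0.31 to 0.92 under the assumed models. Those values come from chosen absorption rates and half-lives, not from data on this drug, and counts over the grid are not probabilities. The consequence would stay within exploratory PK in up to 20 patients with no hypothesis test. Adverse events, urinary oxalate and eGFR are untouched.

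The conclusion rests on Table 5 as printed and on the SAP text that could be read. The text of SAP Section 8, listed in the contents as changes to planned analyses, and the separate population PK plan were not available. A definition of the intervals there would only reduce the gap.

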7.3.3. Evaluate the Pharmacodynamic Effect of lumasiran

Analysis of PD parameters (e.g. 24-hour urine oxalate: creatinine ratio, plasma oxalate, urinary glycolate concentrations, plasma glycolate concentrations) will be performed on the PD Analysis Set. The analysis will be performed based upon data from clinical diagnostic PD assay and quantitative PD assay. For all 24-hour urine parameters with the exception of 24-hour oxalate:creatinine ratio, only valid values will be used in the analysis (note: valid is defined as: creatinine ≥ 10 mg/kg, duration of collection 18 to 26 hours, no missing voids and the sample was not collected within 14 days after the most recent dialysis session, if applicable).

Data will be summarized descriptively (n, mean, SD, SEM, median, quartiles, minimum and maximum) at baseline at each post-baseline scheduled visits. Tabular summaries of actual value, change from baseline and percent change from baseline will be generated at each

scheduled visit. Plots of the mean (+/-SEM) of actual values and percent change will also be generated. Per-patient plots of actual values over time will be generated.

For urine oxalate: creatinine ratio and plasma oxalate, the maximum mean reduction from baseline over time will be summarized descriptively.

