6.3. Concomitant Medications

Use of concomitant medications will be recorded on the patient's eCRF as specified in the Schedule of Assessments (see [Table 1](#)). This includes all prescription medications, herbal preparations, over the counter medications, vitamins, and minerals. Any changes in medications during the study will also be recorded on the eCRF.

Standard vitamins and topical medications are permitted. However, topical steroids must not be applied anywhere near the injection site(s) unless medically indicated. Any treatment for an injection site reaction must be prescribed by the investigator or his/her designee.

Any concomitant medication that is required for the patient's welfare may be administered by the Investigator. However, it is the responsibility of the Investigator to ensure that details regarding the medication are recorded on the eCRF. Concomitant medication will be coded using an internationally recognized and accepted coding dictionary.

Patients may be treated for PH1 according to local standard of care. Patients can continue their current standard of care regimen, including hyperhydration, crystallization inhibitors, and/or pyridoxine therapy during the study. Standard of care treatment may be adjusted in accordance with clinical judgement.

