8.2.5. Pharmacodynamic Analysis

PD analysis will be based on the change from baseline over the course of the study in the following PD parameters:

- eGFR
- 24-hour urinary oxalate corrected for BSA
- Urinary glycolate excretion
- Plasma oxalate concentration

- Plasma glycolate concentration
- 24-hour and spot urinary oxalate:creatinine ratio

The PD parameters will be summarized using descriptive statistics for actual results and relative to baseline for each follow-up time points.

For the parameter eGFR, the change from baseline over the course of the study will be summarized using descriptive statistics for actual results and relative to baseline for each follow-up time points.

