7.2. Secondary Endpoints

7.2.1. Evaluate the pharmacodynamic effect of lumasiran on urinary oxalate excretion

The analysis of 24-hour urinary oxalate excretion corrected for BSA will be based upon the results that meet the validity criteria (i.e., creatinine excretion ≥ 10 mg/kg, duration of collection 18 to 26 hours, no missing voids and the sample was not collected within 14 days after the most recent dialysis session, if applicable). The analysis will be generated separately based upon data from laboratories using a clinical diagnostic PD assay or quantitative PD assay.

Correlations between the assays will be performed comparing oxalate values, 24-hour urinary oxalate corrected for BSA, change and percentage change of 24-hour urinary oxalate corrected for BSA. Per-patient spaghetti plots may also be generated to compare the results over time.

24-hour urinary oxalate (mmol/24h/1.73m²) corrected for BSA at each visit per patient is calculated as follows:

$$[\text{Urine oxalate concentration (umol/L)/1000 (umol/mmol)}] * [\text{24hr urine volume (mL)/1000 (mL/L)}] * [\text{24 hours/actual collection hours}] * 1.73 / (\text{BSA})$$

where BSA=square root (mean height (cm)*weight (kg)/3600) at the visit.

Data will be summarized descriptively at baseline and at each post-baseline visit. Tabular summaries will include actual value, change from baseline and percent change from baseline at each scheduled visit. Per-patient figures and mean (+/-SEM) plots over time of the actual values, change from baseline and percent change from baseline will be generated. A table of the maximum percent reduction per patient will also be generated.

An analysis of the percentage of time at or below 1.5 x ULN will also be summarized. For each patient, the percentage of time will be calculated as follows:

$$\text{Percentage of time at or below 1.5x ULN} = \frac{\text{cumulative months at or below 1.5 x ULN}}{\text{cumulative months of valid assessments}} * 100$$

where cumulative months at or below 1.5x ULN will be defined as the summation across all intervals that met the threshold of at or below 1.5x ULN and cumulative months of valid assessments will be defined as the summation across all valid post-baseline collections. In order to quantify the months at or below 1.5x ULN, a linear interpolation method will be used to determine the bookend dates at which the patient crossed into the threshold and crossed out of the threshold.

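### SAP 7.3.3 names urinary glycolate concentration for analysis, while the exploratory endpoint is urinary glycolate excretion and no derivation of excretion is given

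*SAP*

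**What the plan says.** SAP 3.2.3 gives the exploratory PD endpoint as "Change from baseline over the course of the study in the following PD parameters: urinary glycolate excretion, plasma oxalate concentration, plasma glycolate concentration", followed by the urine oxalate:creatinine ratio. Protocol 3.3 lists the same endpoint, and the analysis list in protocol 8.2.5 has the entry "Urinary glycolate excretion". In all three places glycolate in urine is an excretion, and only the plasma analytes are called concentrations.

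SAP 7.3.3 gives its PD parameters in a list that opens with e.g. and ends "urinary glycolate concentrations, plasma glycolate concentrations) will be performed on the PD Analysis Set". It then states "Tabular summaries of actual value, change from baseline and percent change from baseline will be generated at each" scheduled visit. Apart from the 24-hour oxalate:creatinine ratio, 24-hour urine parameters are limited to valid collections: "creatinine ≥ 10 mg/kg, duration of collection 18 to 26 hours, no missing voids", plus a dialysis condition.

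For oxalate, SAP 7.2.1 provides a full derivation: "24-hour urinary oxalate (mmol/24h/1.73m²) corrected for BSA at each visit per patient is calculated as follows", with terms for urine volume, collection time and body surface area. SAP 7.2.2 also uses urine volume, for measured creatinine clearance. The available SAP text has no corresponding derivation for glycolate.

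**The concern.** Excretion is an amount. Concentration is that amount divided by the volume of urine it was passed in. The two move together only if volume stays constant, and the plan gives reasons why it may not. Protocol 6.3 says "Patients can continue their current standard of care regimen, including hyperhydration, crystallization inhibitors, and/or pyridoxine therapy during the study", and the same section allows standard of care to be adjusted on clinical judgement. Baseline is taken from the parent study (SAP 5.3), enrolment may follow up to 12 months after that study, and treatment may last up to 54 months, so there is ample time for fluid intake to change.

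Protocol 1.5 expects glycolate to rise under the drug, as the consequence of suppressing glycolate oxidase. A variable that depends on dilution could mask or exaggerate that rise. With at most 20 patients, tabulated by initial regimen, individual changes in volume may not average out.

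**Working it through.** The plan states no figure on this point, so there is none to reproduce. The check has three steps.

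**1. Wording, side by side**

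| Place | Urinary glycolate described as |
|---|---|
| Protocol 2.3, objective | excretion |
| Protocol 3.3, endpoint | excretion |
| Protocol 8.2.5, analysis | excretion |
| SAP 3.1.3, objective | urinary glycolate, unspecified |
| SAP 3.2.3, endpoint | excretion |
| SAP 7.3.3, analysis | concentration |

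**2. What a concentration would show**

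Concentration = excretion / volume. Relative to baseline, therefore, concentration ratio = excretion ratio / volume ratio. The volume and excretion ratios below are assumptions, since the documents give no urine volumes.

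| True excretion | Volume | Calculation | Change in concentration |
|---|---|---|---|
| x1 | x0.5 | 1/0.5 - 1 | +100% |
| x1 | x0.75 | 1/0.75 - 1 | +33.3% |
| x1 | x1.25 | 1/1.25 - 1 | -20.0% |
| x1 | x1.5 | 1/1.5 - 1 | -33.3% |
| x1 | x2 | 1/2 - 1 | -50.0% |
| x2 | x0.75 | 2/0.75 - 1 | +166.7% |
| x2 | x1.5 | 2/1.5 - 1 | +33.3% |
| x2 | x2 | 2/2 - 1 | 0% |

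The validity criteria do not alter this. They test whether a collection is complete. A complete collection can still be dilute or concentrated.

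**3. Whether the oxalate formula removes the effect**

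SAP 7.2.1 applied to glycolate: (C/1000) x (V/1000) x (24/hours) x 1.73/BSA. Assume a BSA of 1.2 m² and a 24-hour collection, with the same output in two volumes:

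- C = 1000 umol/L, V = 2000 mL: 1 x 2 x 1 x 1.73/1.2 = 2.883 mmol/24h/1.73m²
- C = 666.7 umol/L, V = 3000 mL: 0.6667 x 3 x 1 x 1.73/1.2 = 2.883 mmol/24h/1.73m²

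Concentration falls by a third and the derived excretion does not change. The time term is needed as well: over the valid range of 18 to 26 hours it runs from 24/18 = 1.333 to 24/26 = 0.923.

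**The case against.** The strongest reply is that 7.3.3 is loosely worded and the authors meant excretion. Four things support it.

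- The list is introduced by e.g. and is visibly incomplete: it omits the spot oxalate:creatinine ratio. It does not rule out an excretion analysis.
- Protocol 7.2 also refers to oxalate and glycolate concentrations in urine and blood, yet urinary oxalate is plainly analysed as excretion. The word may be shorthand for what the laboratory assays.
- Section 7.3.3 applies the completeness criteria to 24-hour urine parameters other than the oxalate:creatinine ratio. That fits an intended amount better than a concentration.
- SAP Section 8, where changes from the protocol are to be recorded, was not in the text available for this review. A declared switch to concentration cannot be excluded.

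All of this bears on intent, and it stands to that extent. It does not supply a derivation: a programmer working from 7.3.3 as written would tabulate concentration.

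A reader might also infer that the on-target marker, or the monitoring of a glycolate risk, is lost. The documents do not support that. Plasma glycolate is a separate endpoint analysed in the same section and does not depend on urine volume. Protocol 1.5 rates the risk from raised glycolate as low, and no dosing or stopping rule in the documents uses urinary glycolate.

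**Conclusion.** The point holds as an inconsistency in the current text of the two documents. If 7.3.3 is followed literally, the tabulated variable is not the stated endpoint. The direction of the distortion is certain at constant output: more urine, lower concentration. Its size is unknown. The -33% and +100% figures rest on assumed volumes of 1.5 and 0.5 times baseline, and nothing in the documents shows that changes of that order occur.

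It would go too far to conclude that glycolate excretion will not be estimated, or that volume changes will be reported as changes in glycolate output. The illustrative list and the validity filter leave room for an excretion analysis that was meant but not written down.

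The consequence is modest. The endpoint is exploratory, the PD summaries are descriptive, and the sample size rests on no power calculation. The correction is still worth making, because it is cheap and removes a doubt about what the glycolate tables measure.

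**What to change.** In SAP 7.3.3, replace urinary glycolate concentrations with 24-hour urinary glycolate excretion on valid collections, and state the formula:

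glycolate concentration x 24-hour urine volume x 24 / actual collection hours, with the unit conversions of SAP 7.2.1.

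Multiplying by 1.73/BSA, as for oxalate, is the natural parallel and would put the two analytes on one scale. The documents do not require BSA correction for glycolate, so the SAP should say whether it applies. Concentration may be kept as a supportive summary. No spot glycolate:creatinine analysis is needed, since no endpoint calls for one.

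If concentration was chosen deliberately, SAP Section 8 should record the departure from protocol 8.2.5 with its reason, and SAP 3.2.3 should be made to agree.

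The cost is a wording change and one derived variable. Volume, collection time, height and weight already enter the oxalate calculation, so no new data are needed.
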